THOMAS JEFFERSON UNIVERSITY
Kimmel Cancer Center

Detection of high grade prostate cancer with subharmonic ultrasound imaging, A pilot study.

Principal Investigators:	[name] Department of Radiology Thomas Jefferson University [name] [contact]	[name] Department of Radiology Thomas Jefferson University [name] [contact]
Co-Investigator(s):	[name] Department of Urology [name] Department of Urology [name] Department of Urology	
Funding Sponsor:	NIH R21CA202214	
Regulatory Sponsor:	[name] PhD	
IND Number:	112,241	
Study Product:	Definity	
Protocol Number:	15F.607	

Version:	Date:
1.0	11/2015
1.1	11/2016
1.2	12/01/17

CONFIDENTIAL

This document is confidential and the property of THOMAS JEFFERSON UNIVERSITY. No part of it may be transmitted, reproduced, published, or used by other persons without prior written authorization from the study sponsor.

Study Summary

Title	Detection of high grade prostate cancer with subharmonic ultrasound imaging, A pilot study
Short Title	Using Contrast-enhanced Ultrasound (CE-TRUS) to Identify Aggressive forms of Prostate Cancer
Protocol Number	
Phase	Phase II clinical study – classified as Phase II because the goal is to demonstrate that imaging of the prostate with CEUS is improved with the use of subharmonic imaging
Methodology/Study Design	Pilot cohort study of patients scheduled for prostate biopsy
Study Duration	two years
Study Center(s)	Single-center
Objectives	
 1. To implement SHI technology on a transrectal probe suitable for prostate imaging and biopsy 2. To demonstrate visualization of prostatic vascularity using subharmonic contrast-enhanced imaging. 3. To provide a preliminary estimate of the diagnostic accuracy of contrast-enhanced subharmonic imaging for detection of clinically significant PCa.
Number of Subjects	55 subjects (5 controls and 50 patients)
Diagnosis and Main Inclusion Criteria	
 1. Patients who are scheduled for prostate biopsy 2. and who are able to undergo CEUS
Study Therapy, Dose, Route, Regimen	The study will involve infusion of the ultrasound microbubble contrast agent Definity immediately prior to a prostate biopsy procedure.
Duration of administration and follow-up	The contrast administration will require 10-15 minutes, during which time a transrectal ultrasound study of the prostate will be performed, and a targeted biopsy procedure of the prostate will be performed.
Reference therapy	Conventional 12-core systematic prostate biopsy
Statistical Methodology	Computation of sensitivity and specificity for detection of clinically significant prostate cancer with conventional 12 core prostate biopsy as the reference standard. No further statistical testing will be performed as this is a preliminary study, designed to demonstrate the feasibility of subharmonic imaging of the prostate and to obtain an estimate of the diagnostic accuracy of CEUS with subharmonic imaging of the prostate.

Schema
	
Subharmonic imaging software will be expanded to work with an endorectal probe on an FDA approved ultrasound imaging system
 
↓
 
Patient with elevated PSA or an abnormal rectal exam, or a patient requiring a prostate biopsy on active surveillance
 
↓
 
Scheduled for prostate biopsy
 
↓
 
Has CEUS with subharmonic imaging
 
↓
 
Prostate biopsy with up to 6 targeted cores based upon subharmonic imaging as well as prostate biopsy with 12 standard systematic cores.

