3.0 STUDY DESIGN

3.1 General Design

This study is a pilot phase II clinical trial of 55 patients (5 controls and 50 patients) over the course of 2 years. Experimental software used for subharmonic imaging of other body parts will be adopted to work with the transrectal prostate probe of an FDA approved ultrasound system, specifically the IC5-9D transducer on the Logiq E9 system (GE Healthcare; Milwaukee, WI). In vitro testing will be performed on 5 patients to ensure that the power output of the transducer with the new subharmonic software is within the FDA approved limits for the system power output. After in vitro optimization of the subharmonic mode for imaging, we will conduct a pilot clinical trial of 50 patients over 2 years. All participants will be evaluated with contrast-enhanced transrectal ultrasound (CE-TRUS) prior to prostate biopsy. Subharmonic imaging of the CE-TRUS study will be used to direct targeted biopsy of the prostate with up to 6 biopsy cores. This will be followed by a conventional systematic biopsy of the prostate with 12 cores.

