6.2 Study Interpretation

The peripheral zone of each prostate will be rated for suspicion of PCa at 12 sites, including medial and lateral component of each sextant. A 5-point rating score will be assessed in real-time by the examining physician for each ultrasound technique. These scores have been previously described and validated,⁸² with proven utility for predicting the risk of malignancy in prior studies.[Error! Bookmark not defined.](#)[Error! Bookmark not defined.](#) A maximum of 6 sites will be identified as the most suspicious areas on SHI; targeted biopsy specimens will be obtained from these sites under ultrasound guidance during contrast-enhanced imaging. If fewer sites are identified, fewer targeted biopsy cores may be obtained.

The interpretation of CEUS studies will follow a 12 part extended sextant grid as demonstrated in the illustration below:

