7.0 STATISTICAL PLAN

7.1 Sample Size Determination

The study is a pilot study, for the purpose of generating preliminary data for a future grant submission. The study is not powered to demonstrate any specific accuracy of CEUS, but rather to accumulate several demonstration cases of SHI in high grade prostate cancer.

Based upon our past experience we expect approximately 30% of our patients to be positive for prostate cancer and half of these (15%) to have a diagnosis of high grade disease. Thus, in a population of 50 patients, the mean expected number of patients with high grade disease would be 7.5. Using an exact binomial probability distribution, the probability of finding at least 5 patients in this sample with high grade disease is 88%. The probability of finding 3 or fewer patients with high grade disease is 4.6%. The probability of not finding a single patient with high grade disease is 0.03%. Thus, the sample size of $n=50$ provides a greater than 95% probability of demonstrating the performance of SHI in at least 3 patients with high grade prostate cancer.

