7.2 Statistical Methods

Rough estimates of the sensitivity and specificity of SHI for high grade disease may be obtained if there are sufficient patients with high grade disease. No additional statistical analysis will be performed

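### With the 12 systematic cores as the only reference standard, high-grade cancer proven only in an SHI-targeted core counts as no disease, and no planned output would show it

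*Combined protocol and SAP*

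**What the plan says.** The Statistical Methodology row of the Study Summary is the only place that names a reference standard: "Computation of sensitivity and specificity for detection of clinically significant prostate cancer with conventional 12 core prostate biopsy as the reference standard". The reference row of the same table also lists the 12-core systematic biopsy.

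The targeted cores are a separate set, taken first. Section 3.1 states "Subharmonic imaging of the CE-TRUS study will be used to direct targeted biopsy of the prostate with up to 6 biopsy cores", and then "This will be followed by a conventional systematic biopsy of the prostate with 12 cores". Section 6.2 says where they come from: "A maximum of 6 sites will be identified as the most suspicious areas on SHI". It allows fewer cores when fewer sites are found.

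Section 3.2, item b, makes sensitivity and specificity a primary endpoint but names no reference. Section 7.2 names none either: "Rough estimates of the sensitivity and specificity of SHI for high grade disease may be obtained", provided there are enough high-grade patients, followed by "No additional statistical analysis will be performed". No section says how targeted-core histology enters the accuracy table, and none plans a count by core type.

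**The concern.** Section 1.5 proposes SHI as a way to target biopsies so that clinically significant cancer is found more effectively. A high-grade cancer found by a targeted core and missed by the 12 systematic cores is therefore a result the technique is meant to produce. Under the stated reference, that man is disease-negative despite histological proof of disease. If his targeted site counts as SHI-positive, a correct detection is charged to SHI as a false positive and lowers specificity. It adds nothing to sensitivity.

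Section 7.1 says the data are to support a future grant application. A reader of the planned 2x2 table could not tell whether any such man occurred or how far he moved the estimates.

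**Working it through.** **The plan's own figures.** Section 7.1 assumes 50 patients with a 15% high-grade rate, so that "the mean expected number of patients with high grade disease would be 7.5" (50 × 0.15 = 7.5). Exact binomial probabilities:
- P(X ≥ 5) = 0.888 (stated 88%)
- P(X ≤ 3) = 0.0460 (stated 4.6%)
- P(X = 0) = 0.85^50 = 0.000296 (stated 0.03%)

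These reproduce. The sample size is not in question.

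**Inputs for the illustration.** All are assumptions except n = 50, because the documents give no accuracy figures for SHI in the prostate:
- per-patient analysis of 50 men
- 7 high-grade on systematic cores (7.1 expects 7.5), 5 of them SHI-positive
- 43 men negative on systematic cores, including 13 false positives who have no high-grade cancer in any core
- t further men among the 43 with high-grade cancer in a targeted core only, all SHI-positive

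**Formulas.**
- 12-core reference: sensitivity = 5/7; specificity = (43 − 13 − t)/43 = (30 − t)/43
- Any-core reference: sensitivity = (5 + t)/(7 + t); specificity = (30 − t)/(43 − t)

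**Results.**

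| t | 12-core sensitivity | Any-core sensitivity | 12-core specificity | Any-core specificity |
|---|---|---|---|---|
| 0 | 5/7 = 71.4% | 5/7 = 71.4% | 30/43 = 69.8% | 30/43 = 69.8% |
| 1 | 5/7 = 71.4% | 6/8 = 75.0% | 29/43 = 67.4% | 29/42 = 69.0% |
| 2 | 5/7 = 71.4% | 7/9 = 77.8% | 28/43 = 65.1% | 28/41 = 68.3% |

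The specificity gap is 1.6 points at t = 1 and 3.2 at t = 2. Varying the other false positives from 20 down to 5 gives 1.2 to 2.0 points at t = 1 and 2.4 to 4.1 at t = 2. The sensitivity gap is 3.6 points (75.0 − 71.4) and 6.4 points (77.8 − 71.4).

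**Sampling error for comparison.** Exact 95% intervals are 29.0% to 96.3% for 5/7 and 49.1% to 79.0% for 28/43. Both are far wider than the gaps.

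**How likely is at least one such man?** The rate is unknown. If it were 1%, 2% or 5% of men (assumed), the chance of at least one in 50 is 1 − (1 − r)^50 = 39%, 64% or 92%.

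Section 1.5 does not settle the rate. It reports that targeted cores were about twice as likely to be positive, but that is per core. It also reports that targeting on harmonic imaging alone detected high-grade cancer less well per patient than 12 cores. A method that is weaker overall can still find cancers the other misses, and neither result concerns SHI.

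**The case against.** **The 12-core reference is deliberate and defensible.** This stands. Systematic sites are fixed without regard to SHI, whereas targeted cores come only from SHI-flagged sites. If a targeted site counts as SHI-positive, adding those cores can only raise sensitivity and specificity or leave them unchanged. A reader might infer that an any-core reference should replace the 12-core one. The documents do not support that: it would build the index test into the reference.

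**Nothing in the plan turns on it.** This also stands. The study is not powered for accuracy, 7.2 promises only rough estimates, and no decision rule would change.

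**The sponsor may intend otherwise.** Item b of 3.2 refers to accuracy after the biopsy procedure, and the schema places both core types in that procedure. If targeted-core histology were itself the index test, a targeted-only cancer would be a false positive by design. Neither intention is written down, and the one stated rule gives the classification described.

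**A descriptive count is not barred.** This is arguable, since the Summary excludes only further testing. But 7.2 is worded more broadly, and no count is planned.

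**The 12-core figures might instead flatter SHI.** A reader might infer this if a targeted site fell below the SHI cut-off, so that the man became a true negative hiding an SHI miss. It cannot be excluded, because 6.2 sets no cut-off on its 5-point score. It is a strained reading, however, because targeted sites are by definition those SHI found most suspicious.

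**The cost is understated.** Partly right. The text does not say that histology is recorded by core type, and the case report forms cited in 9.3 are not in the text available. Both tables also need an SHI cut-off and a definition of high grade. Those gaps, like unit of analysis and blinding, are separate matters, and the planned table needs the cut-off and the definition in any case.

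**Conclusion.** The point holds as a cheap improvement. By the stated rule, a man with high-grade cancer proven only in a targeted core is disease-negative and, if his targeted site counts as SHI-positive, an SHI false positive. No planned output would reveal him. In the illustration, one or two such men put 12-core specificity about 1.6 or 3.2 points below the any-core figure, and sensitivity about 3.6 or 6.4 points below. This rests on assumed counts, a per-patient table and an unknown number of such men.

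A reader might infer that the planned estimates are seriously biased. The documents do not support that: the number of such men may be zero, and the shifts are small beside sampling error. Nor would the change reveal high-grade cancers missed by every core, which remain invisible under either reference. The gain is that the pilot could show whether SHI finds high-grade cancers that the 12 cores miss.

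**What to change.** In the Study Summary and 7.2:

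1. Keep the 12-core reference as the main analysis and state that it is per patient.
2. Record histology separately for targeted and systematic cores.
3. Report the number of men with high-grade cancer found by both core types, by targeted cores only, by systematic cores only and by neither. Give the SHI score of each targeted-only man.
4. Beside the main table, place a descriptive 2x2 table counting high-grade cancer in any core as disease-positive. Label it as favouring SHI, because only SHI-flagged sites receive extra cores, and as unable to show cancers missed by all cores.
5. State in 7.2 that these descriptive outputs are not excluded by "No additional statistical analysis will be performed".

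The cost is a few sentences, two descriptive tables and confirmation that pathology is recorded by core type. No extra cores, patients or staff are needed. The downside is that the any-core table is optimistic for SHI and could be quoted alone, so it should never be reported without the 12-core table and the count by core type.

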1.0 INTRODUCTION

This document is a protocol for a human research study. This study is to be conducted according to US and international standards of Good Clinical Practice (FDA Title 21 part 312 and International Conference on Harmonization guidelines), applicable government regulations and Institutional research policies and procedures.

1.1 Specific Aims and Hypothesis

1. To implement SHI technology on a transrectal probe suitable for prostate imaging and biopsy
2. To demonstrate visualization of prostatic vascularity during subharmonic contrast enhanced imaging of the prostate.
3. To provide a preliminary estimate of the diagnostic accuracy of contrast-enhanced subharmonic imaging for detection of prostate cancer.

1.2 Background and Rationale

Prostate cancer (PCa) is the most prevalent cancer among American males, with an estimated 3,922,600 living PCa patients.¹ Biochemical screening with serum prostate specific antigen (PSA) results in the detection of many small cancers such that “the risk of being diagnosed with PCa is increasingly greater than the risk of dying of it”.² Thus, although PCa will account for 27% (233,000/855,220) of all new cancer diagnoses among American males in 2014, PCa is estimated to be directly responsible for only 9.5% (29,480/310,010) of cancer related deaths among American males.³ PCa has been likened to the two faces of Janus: “one benevolent face of small, indolent tumors, abundant among middle-aged and elderly men” and a second “grim face of a great killer, being the second most common cancer-related cause of death within the EU and in the US”.⁴ This dichotomy in the progression and prognosis of PCa creates a dilemma for both physician and patient in deciding between definitive therapy of a potentially lethal disease and expectant management of a potentially indolent disease. Simply stated, the PCa treatment dilemma is related to our inability to distinguish indolent from aggressive PCa at the time of diagnosis.

Two recent clinical trials have sparked an intense controversy related to the benefit of screening and treatment of PCa. The Prostate, Lung, Colorectal, and Ovarian (PLCO) Cancer Screening Trial failed to show a mortality benefit from screening and treatment of PCa.⁵ The European Randomized Study of Screening for PCa (ERSPC) suggests that with the current standard of care, 1410 men must be screened and 48 additional cases of PCa treated to prevent

one death.⁶ Both studies suggest that overdiagnosis and overtreatment of insignificant cancer is a major drawback of PCa screening, and point to the need for better diagnostic tools to identify clinically significant PCa.⁷ Based upon the data from these trials, the U.S. Preventive Services Task Force (USPSTF) has issued a grade “D” recommendation against PSA-based screening.⁸

Various treatment options are available to the patient with a new diagnosis of PCa. Aggressive therapy with surgery or radiation constitutes the traditional therapy for localized PCa, with the goal of treating the entire prostate to eradicate the cancer. However, both radical prostatectomy and radiation therapy can be associated with substantial morbidity, including sexual impotence, urinary incontinence and injury to adjacent organs.^{9,10} Expectant management without curative therapy has demonstrated favorable 15-20 year follow-up results for localized, low-grade PCa.^{11,12} Prospective cohort studies suggest that aggressive treatment for PCa may be deferred until there is evidence of cancer progression.¹³ For men with “favorable risk” PCa, defined as low volume disease (< 0.5 ml) with a Gleason score below 7, active surveillance (AS) results in similar survival as definitive therapy,¹⁴ and conservative management is associated with a 50% lower incidence of incontinence and impotence as compared to radical prostatectomy.¹⁵ A major barrier to the widespread adoption of AS is the lack of an accurate non-invasive diagnostic test to prospectively identify those patients with aggressive “clinically significant” cancer whose disease will progress without definitive therapy. Patients on AS therefore require a periodic invasive biopsy for tissue diagnosis. A technique that could improve the accuracy of diagnostic ultrasound for the diagnosis of clinically significant PCa would facilitate wider use of AS.

Contrast-Enhanced Imaging of Prostate Cancer

As prostate imaging is necessary for biopsy guidance in the diagnosis of PCa, much research has focused on optimization of imaging techniques for PCa detection. Our group has focused primarily on prostate imaging with microbubble ultrasound contrast agents, as ultrasound is the least expensive and most commonly used modality for guidance of prostate biopsy. When exposed to an ultrasound pulse at some fundamental frequency (f_0), microbubbles act as nonlinear oscillators, generating significant energy components which span the range of frequency emissions from subharmonics through ultraharmonics.¹⁶ While conventional ultrasound processes received echoes at the fundamental frequency (f_0), contrast-enhanced ultrasound imaging is based upon received echo signals in the harmonic ($2f_0$, $3f_0$, etc) or subharmonic ($1/2 f_0$, $1/3 f_0$, etc) range. Since microbubble contrast agents remain intravascular, contrast-enhanced transrectal ultrasound (CE-TRUS) with harmonic imaging (HI) or subharmonic imaging (SHI) selectively images vascularity within the prostate.

Pathologic studies demonstrate a clear association of microvessel density with the presence of PCa,¹⁷ with metastatic disease,¹⁸ with disease stage¹⁹ and with disease-specific survival.^{20,21} Although microvessels are below the resolution of conventional ultrasound Doppler imaging, CE-TRUS provides a practical solution to imaging the microvasculature. Clinical studies using HI have demonstrated that enhancement of the prostate with CE-TRUS is related to increased microvessel density,^{22,23} that CE-TRUS can improve detection of PCa,^{24,25} and that CE-TRUS can increase cancer detection with fewer biopsy cores.^{26,27} We review preliminary results with CE-TRUS HI and SHI below, but note that there are no published studies using SHI of the prostate.

1.3 Study Therapy

Since the subjects in this study are scheduled to have prostate biopsy as part of their standard of care, the only study related test that will be performed is a contrast-enhanced ultrasound with subharmonic imaging. The proposed ultrasound contrast agent for the current study, Definity™, (Perflutren Lipid Microsphere, Lantheus Medical Imaging, Inc; N. Billerica, MA), is a microbubble contrast agent that demonstrates enhancement of the prostate on both grayscale and Doppler imaging. Definity is a sterile, non-pyrogenic suspension of liposome-encapsulated perfluoropropane microbubbles. This contrast agent is composed of a blend of three phospholipids contained in a matrix of sodium chloride, propylene glycol and glycerin in water. The contrast agent is supplied in a vial that contains the phospholipids and perfluoropropane gas. The microbubble agent is prepared by shaking the standard size vial with the aid of a shaking device (Vialmix; ESPE, Seefeld, Germany). Based upon our previous experience with Definity, two vials of Definity will be mixed and diluted in 50 ml of normal saline, yielding a concentration of 49.4 µl/ml. For the purpose of contrast-enhanced imaging, Definity will be infused over approximately 10-12 minutes, during which time pulse inversion harmonic and flash replenishment imaging will be performed. Definity remains stable within the circulation for 3 to 6 minutes after infusion; all contrast-enhanced procedures will be completed during the infusion time.

1.3 Clinical Data – Breast and Liver

Feasibility studies of this new SHI mode have been conducted *in vitro* and *in vivo* by our group^{28,29} as well as others^{30;31,32,33,34,35;36;37;38}. Researchers at Jefferson produced the first ever *in vivo* grayscale SHI images (of canine kidneys) using a modified US scanner. We also produced the first ever *in vivo* human grayscale SHI images, demonstrating (in 14 women with 16 breast lesions) that SHI can detect the slow, small volume blood flow associated with breast tumor angiogenesis in humans.³⁹

Fig. 1 presents an example of a fibroadenoma imaged after administration of Optison with power Doppler imaging (PDI) and in SHI mode (transmitting at 4.4 MHz and receiving at 2.2 MHz; optimized for SHI) using a modified Logiq 9 scanner (GE Healthcare, Milwaukee, WI). Notice, the almost complete lack of signal from non-vascular tissue, and that the internal morphology of the tumor vascularity was visualized better with SHI than with contrast enhanced PDI.

Figure 1. Fibroadenoma (arrows) imaged in PDI mode (a) and in SHI mode (b) after injection of contrast.

Fig. 2 shows a breast lesion with benign ductal microcalcifications and fibrocystic changes. Branching vessels within and around the lesion are depicted in finer detail with SHI (Fig 3b) and without the color blooming of contrast enhanced PDI (Fig 3a). Finally, SHI depicts neovessels ($\sim 20\text{-}40\mu\text{m}$ diameter⁴⁰) not observed with conventional imaging.

[figure not shown]

Figure 2. Benign ductal microcalcifications and fibrocystic changes (arrows) depicted with contrast PDI (a) and with SHI (b).

More recently we have focused on translating grayscale SHI into human clinical trials in the breast and liver^{41,42} and on improved processing of SHI images.⁴³ We have introduced the concept of CMI-SHI, where the inflow of contrast bubbles in tumor neovessels is reconstructed by temporal maximum intensity projection of pixels traced from successive image frames.^{44;45} A dynamic cumulative maximum intensity display for subharmonic imaging (CMI-SHI) was developed using a new automated kernel tracking algorithm by identifying motion induced displacements. As demonstrated by the receiver operating characteristic analysis in Fig 3, the area under the curve for diagnosis of breast cancer was greatest for dynamic CMI-SHI (0.90) and was

[figure not shown]

Figure 3. ROC curves for four of the imaging modalities; (GS: grayscale).

significantly better than for mammography ($p = 0.031$). With regard to tissue perfusion, we have developed a novel method for deriving quantitative estimates of tissue perfusion, based on *in vivo* grayscale SHI⁴⁶ as an alternative to the well-known destruction/reperfusion technique.⁴⁷ A modified Logiq 9 scanner operating in SHI mode was used to measure renal perfusion. Fractional blood volumes were estimated from subharmonic signal intensities from blood in tissue.^{48,49} Perfusion was estimated from the initial slope of the SHI time intensity curve and correlated with the reference standard neutron activation assay technique ($r = 0.62$; $p < 0.001$).⁵⁰ Finally, we created parametric images of SHI contrast kinetics, demonstrating increased perfusion in breast cancer relative to benign lesions (0.103 ± 0.030 vs. 0.054 ± 0.017 ; $p = 0.0014$).⁵¹

